6.2. Number of Subjects

Approximately 377 subjects are planned to be dosed in this study:

- Approximately 262 subjects will be dosed in Cohort A.
- Approximately 115 subjects will be dosed in Cohort B.

[figure not shown]
See Section 7 for complete eligibility details and Section 12.1 for complete sample size assumptions.

6.3. Treatment Assignment

All subjects will be administered $9 \pm 1 \text{ mCi} (333 \pm 37 \text{ MBq})^{18}\text{F-DCFPyL}$ Injection followed by PET/CT imaging as illustrated in the schema below. See Section 9.6 Study Drug Administration and Table 3 Schedule of Assessments for complete details.

Figure 1: Study Schema

6.4. Dose Adjustment Criteria

Dosing adjustments of ¹⁸F-DCFPyL Injection are not permitted.

6.5. Study Duration

The duration of subject participation will be from informed consent through ¹⁸F-DCFPyL PET/CT scanning and follow-up visit, a total maximum duration of 58 days.

6.6. Safety Monitoring

An independent Data Monitoring Committee (DMC) will not be used for this open label study. However, safety monitoring will consist of continuously monitoring adverse events on an ongoing basis in accordance with Section 11. A Safety Review Committee, consisting of Sponsor representatives (e.g., Medical Monitor, Clinical Operations designee, Biometrics designee) and at least one active Principal Investigator will also review data on an ongoing basis to assess subject safety, eligibility and baseline characteristics through listings, tables and subject profiles.

6.7. Criteria for Study Termination

The Sponsor reserves the right to terminate the study at any time. In the event of serious, unexpected and related adverse events, the program may be stopped prematurely upon advice from the Safety Review Committee, the Sponsor or upon request from the FDA. In addition, the Sponsor or the Institutional Review Board (IRB) or Ethics Committee (EC) may terminate an investigational site for the following (but not limited to) reasons:

- If any safety issues occur;
- Failure of the Investigator to comply with pertinent International Conference on Harmonisation (ICH) E6 guidelines on Good Clinical Practice (GCP) guidelines and regulations;
- If serious protocol violations occur;

- Submission of knowingly false information from the research facility to the Sponsor, Clinical Monitor, or other party involved in the study;
- Failure of the Investigator to enroll subjects into the study at an acceptable rate as agreed-upon with the Sponsor

 Table 3:
 Schedule of Assessments

	Screening / Baseline	¹⁸ F- DCFPyL Dosing	¹⁸ F- DCFPyL Imaging	Pre- Surgery/Biopsy Follow-Up
	Day-30 to Day 1	Day 1	1-2 Hours Post Dosing	Within 28 Days Post Dosing
Cohorts A and B				
Informed Consent & Eligibility	Х			
Demographics (date of birth, race, ethnicity, height, weight, BMI)	Х			
Medical History (see Section 11.1.1)	Х			
Prior Cancer Medications & Treatments	Х			
Clinical Labs (Hematology, Chemistry) see Table 6	X^1			Х
PSA (Total) & Testosterone	\mathbf{X}^{1}			
Vital Signs (Blood Pressure, Heart Rate, Temperature, Respiratory Rate)	Х	X (pre- dosing)	X (pre- imaging)	Х
12-Lead Electrocardiogram (ECG) (see Section 11.1.4)		X (pre- dosing)	X (pre- imaging)	
¹⁸ F-DCFPyL Administration (see Section 9)		Х		
Whole Body PET/CT (see Section 10.1)			X	
Adverse Events (see Section 11.2.1.1)			X	X ⁵
Concomitant Medications (see Section 8.2)	Х	2	X	Х
Conventional Imaging (CT or MRI, Bone Scan) (see Section 10.1)	X ²			
Surgery or Image-Guided Biopsy				X ^{3,6}

Table 3: Schedule of Assessments

	Screening / Baseline	¹⁸ F- DCFPyL Dosing	¹⁸ F- DCFPyL Imaging	Pre- Surgery/Biopsy Follow-Up			
	Day-30 to Day 1	Day 1	1-2 Hours Post Dosing	Within 28 Days Post Dosing			
Subset of Cohort A or B at Johns Hopkins University only for Pharmacokinetic (PK) Analysis							
Blood Collection		X (9) collections) ⁴					

	conections)		
Urine Collection	X (3		
	collections) ⁴		
Whole Body PET/CT		X (3	
		scans) ⁻	

¹ To be collected prior to dosing, if collected on day of dosing. If PSA and testosterone have not been tested within 30 days of study drug injection, a blood draw will be collected prior to dosing.

² If not obtained as standard of care ≤ 6 weeks (Cohort A) or ≤ 4 weeks (Cohort B) prior to Day 1. Na-¹⁸F-PET bone scans conducted at screening must be at least 10 hours prior to dosing (see Section 7.2).

³ Surgery or biopsy to occur at least 12 hours from time of ¹⁸F-DCFPyL dosing but not more than 28 days from dosing. In Cohort B, imaging used to guide biopsy (i.e., CT, MRI) will be submitted to a central core imaging lab.
 ⁴ See Section 10.6 for complete details. Analysis should occur immediately following last sample collected.

⁵ A safety phone call will also occur 7(\pm 3) days post-dosing [if surgery (Cohort A) or biopsy (Cohort B) has not yet occurred] and 21(\pm 7) days post biopsy (Cohort B). See Section 11.2.1.1 for complete details.

⁶ If a subject's planned procedure (RP or biopsy) for prostate cancer changes following ¹⁸F-DCFPyL imaging, the alternate or additional prostate cancer procedure and corresponding histopathology data will be recorded in the electronic case report form (eCRF).

7. SELECTION AND WITHDRAWAL OF SUBJECTS

7.1. Subject Inclusion Criteria

Subjects must meet all of the following inclusion criteria:

All Cohorts:

- 1. Adults ≥ 18 years of age.
- 2. Subjects provide signed informed consent and confirm that they are able and willing to comply with all protocol requirements.
- 3. Histologically confirmed adenocarcinoma of the prostate.

Cohort A Only:

- 4. At least high risk prostate cancer defined by NCCN Guidelines Version 3.2016 (clinical stage \geq T3a or PSA >20 ng/mL or Gleason score \geq 8).⁴⁷
- 5. Scheduled or will be scheduled to undergo radical prostatectomy with PLND.

Cohort B Only:

- 6. Radiologic evidence of local recurrence or new or progressive metastatic disease demonstrated on anatomical imaging (CT, MRI, or ultrasound), whole-body bone scan (^{99m}Tc-MDP or Na¹⁸F) within 4 weeks of Day 1.
- 7. If prior treatment with radiation or ablative therapy, evidence of recurrence outside the confines of prior treated site(s).
- 8. Scheduled or will be scheduled for percutaneous biopsy of at least one amenable lesion.

7.2. Subject Exclusion Criteria

Subjects meeting any of the following exclusion criteria are not eligible for this study:

All Cohorts:

- 9. Subjects administered any high energy (>300 KeV) gamma-emitting radioisotope within five physical half-lives, or any IV iodinated contrast medium within 24 hours, or any high density oral contrast medium (oral water contrast is acceptable) within 5 days, prior to study drug injection.
- 10. Subjects with any medical condition or other circumstances that, in the opinion of the investigator, compromise obtaining reliable data, achieving study objectives, or completion.

Cohort A Only:

11. Patients with prior androgen deprivation therapy or any investigational neoadjuvant agent or intervention

Cohort B Only:

- 12. Prior radiation or ablative therapy to intended site of biopsy, if within the prostate bed.
- 13. Initiation of new systemic therapy for recurrent and/or progressive metastatic disease since radiographic documentation of recurrence/progression.

7.3. Subject Withdrawal Criteria

A patient may withdraw from the study at any time for any reason without prejudice to his/her future medical care by the physician or at the study site. Likewise, the Investigator and/or Sponsor have the right to withdraw patients from the study. Subjects may be discontinued for any of the following reasons:

- Significant protocol violation or noncompliance (e.g., initiation of treatments forbidden per Section 7.2)
- Adverse event that precludes further study participation
- Best medical interest of the patient (Investigator decision)
- Sponsor terminates the study
- Subject requests to be withdrawn from the study
- Subject is lost to follow-up
- Death

Should a subject withdraw, all efforts will be made to complete the required study procedures as thoroughly as possible.

Data will be collected for all withdrawn subjects up until the time of discontinuation. The reason for discontinuation from the study will be recorded in the subject's eCRF.

8. TREATMENT OF SUBJECTS

8.1. Description of Study Drug

A single administration of ¹⁸F-DCFPyL Injection (PyL) will be administered 1-2 hours prior to PET/CT imaging on Day 1.

	Investigational Product
Product Name	¹⁸ F-DCFPyL INJECTION (PyL)
Dosage Form	Sterile solution for intravenous injection
Unit Dose	$9 \pm 1 \text{ mCi} (333 \pm 37 \text{ MBq})$
Route of Administration	Intravenous catheter placed in an antecubital vein or an equivalent venous access
Physical Description	Colorless, particle-free solution

 Table 4:
 Investigational Product

8.2. Concomitant Medications and Procedures

All concomitant medications and medical procedures that occur within 7 days of consent will be recorded.

Any new prostate cancer therapy is *strictly prohibited* from time of dosing (Day 1) to surgery (Cohort A), or from time of radiographic documentation of disease progression to biopsy (Cohort B). If a subject reports having received a new prostate cancer therapy (e.g., hormone, drug, biologic, radiologic, or chemotherapy) or alternate medical procedure(s) for prostate cancer, during these time periods, the subject should be discontinued from the study.

Medical procedure(s) and histopathology data for subjects who do not receive the planned protocol procedure but who received alternate or additional medical procedure(s) for prostate cancer will be recorded in the eCRF.

8.3. Treatment Compliance

All ¹⁸F-DCFPyL drug injected will be administered under the supervision of the investigator, or qualified designee. Details of the study drug injection will be captured in each subject's source documents.

8.4. Randomization and Blinding

This is an open-label, non-randomized study. Three independent readers from a central imaging core lab will be given access to ¹⁸F-DCFPyL PET/CT imaging, conventional imaging, and biopsy-guided imaging. The central readers will be blinded to all other clinical information and radiology assessments. Likewise, the Investigator is responsible for ensuring that local pathologists who generate the histopathology results for the primary endpoint remain blinded to all imaging results.

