5. TRIAL ENDPOINTS

5.1. **Primary Endpoints**

- 1. Specificity of ¹⁸F-DCFPyL PET/CT imaging to determine the absence of metastatic prostate cancer within the pelvic lymph nodes relative to histopathology (cohort A)
- 2. Sensitivity of ¹⁸F-DCFPyL PET/CT imaging to determine the presence of metastatic prostate cancer within the pelvic lymph nodes relative to histopathology (cohort A)

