5.2. Secondary Endpoints

- 1. Safety and tolerability (Cohorts A and B combined):
 - a. Treatment-emergent adverse events
 - b. Pre- and post-¹⁸F-DCFPyL PET/CT lab values, ECGs and vital signs
- 2. Sensitivity of ¹⁸F-DCFPyL PET/CT imaging to detect prostate cancer within sites of metastasis or local recurrence relative to histopathology (Cohorts B)
- 3. Comparison of detection rates (Cohorts A and B combined) for lesion counts overall and by location (i.e., bone, lymph nodes, soft tissue, prostate gland) between ¹⁸F-DCFPyL and conventional imaging
- 4. PPV and NPV of ¹⁸F-DCFPyL PET/CT imaging (Cohort A) to predict prostate cancer within the prostate gland and lymph nodes
- 5. PPV of ¹⁸F-DCFPyL PET/CT imaging to predict prostate cancer within sites of local recurrence and other metastatic lesions (cohort B)
- 6. Pharmacokinetic parameters [e.g., C_{max}, area under the curve (AUC), total clearance (CL), steady-state volume of distribution (V_{ss}) and mean residence time (MRT)] (subset of Cohorts A and B combined)

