6. INVESTIGATIONAL PLAN

6.1. Overall Study Design

This is an open-label, non-randomized, Phase 2/3, multi-center study designed to evaluate the safety and diagnostic performance of ¹⁸F-DCFPyL PET/CT imaging to determine the presence or absence of metastatic prostate cancer in subjects with at least high risk prostate cancer who are planned for radical prostatectomy [RP] with pelvic lymph node dissection [PLND]) (cohort A), and subjects with radiologic evidence of local recurrence or new or progressive metastatic disease (cohort B).

Eligible subjects (see Section 7.1 for Inclusion Criteria) will be enrolled in a non-randomized, sequential manner, with competitive enrollment between study sites.

Diagnostic performance characteristics of ¹⁸F-DCFPyL PET/CT imaging will be evaluated using histopathology as the truth standard. See Section 8.4 for details on blinding.

The study will explore changes to clinical management plans based on data before and after ¹⁸F-DCFPyL PET/CT imaging.

This study is planned to be performed in approximately 10 sites in the United States and Canada.

See Figure 1 and Table 3 for the study schema and schedule of assessments.

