#### 4. STUDY DESIGN

## 4.1. Summary of Study Design

This is an open-label, non-randomized, Phase 2/3, multi-center study designed to evaluate the safety and diagnostic performance of F-DCFPyL PET/CT imaging to determine the presence or absence of metastatic prostate cancer in subjects with high risk prostate cancer who were planned for radical prostatectomy with pelvic lymph node dissection (cohort A), and subjects with radiologic evidence of local recurrence or new or progressive metastatic disease (cohort B) who were biopsied if a positive lesion was found on the F-DCFPyL PET/CT scan. The physician has the option to change the planned protocol specified procedure (i.e., RP ePLND for Cohort A subjects and Biopsy for Cohort B subjects) for the subjects based on the F-DCFPyL PET/CT scan. The details of these changes will be collected on the CRF, and these subjects obviating the planned procedure will not be included in any of the primary or secondary endpoints.

Eligible subjects will be enrolled in a non-randomized, sequential manner, with competitive enrollment between study sites. Ten (10) study sites will be used in the U.S. and Canada.

[figure not shown]
Diagnostic performance characteristics of F-DCFPyL PET/CT imaging will be evaluated using histopathology as the truth standard. Three independent readers from a central imaging core lab will be given access to F-DCFPyL PET/CT imaging, conventional imaging, and biopsy-guided imaging. The central readers will be blinded to all other clinical information (i.e. pathology data) and radiology assessments. Likewise, local pathologists who generate the histopathology results for the primary endpoint are blinded to all imaging results.

A change in clinical management questionnaire will be filled out by an independent urologist who is not otherwise a participant of the study. To maintain the blind for imaging, a statistician who is independent from the PyL study team will generate subject listings. A combination of imaging and clinical data will then be posted to a share point site where the independent urologist will review these data and fill out the questionnaire based on the results he sees prior to PyL imaging and then again after PyL imaging. To keep things simple, only imaging data from reviewer 1 will be presented for this assessment to be performed.

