#### **5.5.7.2.** Biopsy

Sensitivity and PPV are defined from imaging results in subjects undergoing a biopsy confirmed by conventional imaging and histology obtained from this biopsy. This will be performed for Cohort B only.

Criteria for Positive PyL Imaging Result	Criteria for Biopsy and Positive Histology
Biopsied Lesion consistent with PSMA Positive uptake on the  F-DCFPyL PET/CT = yes	Pathology result=Positive for prostate cancer

If Cohort =B, imaging and histology are obtained for the biopsy, and the above criteria are not met (Biopsied Lesion consistent with PSMA Positive uptake on the F-DCFPyL PET/CT = no or pathology result = negative) then results = Negative for each respective endpoint.

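### Pathologist blinding is required only for the Cohort A primary endpoint; neither document extends it to the site pathology that sets the truth for Cohort B sensitivity and PPV

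*Protocol*

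**What the plan says.** - **Blinding rule.** Protocol 8.4 requires that "local pathologists who generate the histopathology results for the primary endpoint remain blinded to all imaging results". SAP 4.1 states that "local pathologists who generate the histopathology results for the primary endpoint are blinded to all imaging results".
- **Its scope.** Both primary endpoints (Protocol 5.1, SAP 3.2.1) are specificity and sensitivity in the pelvic lymph nodes of Cohort A.
- **What falls outside it.** Cohort B sensitivity and PPV are secondary endpoints (Protocol 5.2, SAP 3.2.2). So are PPV and NPV for the Cohort A prostate gland.
- **Truth standard.** Under Protocol 6.1, diagnostic performance "will be evaluated using histopathology as the truth standard". Protocol 10.5 and 12.3.1 have the specimens read at the site. SAP 5.5.7.2 counts a Cohort B biopsy as positive when "Pathology result=Positive for prostate cancer". No central or masked pathology review is described.
- **Test result.** The PET call comes from central review (Protocol 12.3.1), separately for each of three readers, who are blinded to pathology (SAP 4.1).
- **Decision rule.** Protocol 12.5.2.2 compares the lower 95% limit with 0.50 and asks for at least two of three readers. SAP 7.7.2 uses a null value of 0.5 for Cohort B.

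**The concern.** The plan accepts that the reference standard should be read without knowledge of the images, but it states that protection for one endpoint only.

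Exposure in Cohort B is plausible. The study is open-label, and the biopsy follows the scan by up to 28 days (Protocol 10.4). Site physicians know the scan, because SAP 4.1 lets them change the planned procedure because of it. SAP 4.1 also describes Cohort B biopsy as conditional on a positive PET lesion; on that wording, the arrival of a biopsy specimen itself tells the pathologist the scan was positive.

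A scanty or equivocal core may then be read towards the PET. The reference standard would no longer be independent of the test, and the Cohort B accuracy estimates would carry a bias that no planned analysis would reveal.

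**Working it through.** **Figures in the plan.** The plan gives no figure for this point. The Cohort A size reproduces: 47.09 positives / 0.20 = 235.5, so 236; 236 / 0.90 = 262.2, so about 262. Nothing below alters it.

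**Assumed inputs, none from the documents.** 100 evaluable Cohort B subjects; 80 truly positive; 10 of the 20 benign lesions PET-positive (FP = 10, TN = 10); a share e = 5-20% of cores equivocal; true sensitivity 0.60, 0.75 or 0.85.

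**Step 1: upper bound.** Suppose every equivocal core is resolved to the PET result and the site read always equals the central read. Then TP' = TP + e·FP, FN' = (1−e)·FN and FP' = (1−e)·FP, with sensitivity' = TP'/(TP'+FN') and PPV' = TP'/(TP'+FP').

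| True sensitivity | TP, FN | Sensitivity', e = 5% | Sensitivity', e = 20% | True PPV | PPV rise, e = 5% to 20% |
|---|---|---|---|---|---|
| 0.60 | 48, 32 | 48.5/78.9 = 0.615 | 50/75.6 = 0.661 | 48/58 = 0.828 | 0.9 to 3.4 points |
| 0.75 | 60, 20 | 60.5/79.5 = 0.761 | 62/78 = 0.795 | 60/70 = 0.857 | 0.7 to 2.9 points |
| 0.85 | 68, 12 | 68.5/79.9 = 0.857 | 70/79.6 = 0.879 | 68/78 = 0.872 | 0.6 to 2.6 points |

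**Step 2: the pathologist could learn only the site read.** Let a be the agreement between the site read and the central reader, assumed unrelated to the truth. Equivocal cores follow the site read:

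- TP' = (1−e)·TP + e·a·(TP+FP)
- FN' = (1−e)·FN + e·(1−a)·(FN+TN)
- PPV' = (1−e)·PPV + e·a

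PPV therefore rises only if a exceeds the true PPV. At true sensitivity 0.75 (PPV 0.857) and a = 0.85, the change is e × (0.85 − 0.857), a fall of 0.04 points at e = 5% and 0.14 at e = 20%.

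Sensitivity at 0.75 and e = 10%:

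- a = 1: 61/79 = 0.772
- a = 0.90: 60.3/78.6 = 0.767
- a = 0.85: 59.95/78.4 = 0.765

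Sensitivity rises whenever a/(1−a) exceeds PPV/(1−NPV). On these inputs that ratio is 0.828/0.762 = 1.09, 0.857/0.667 = 1.29 and 0.872/0.545 = 1.60 for the three rows, so a must exceed about 0.52, 0.56 and 0.62. The upward direction is much safer for sensitivity than for PPV.

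**Step 3: the decision against 0.50.** The normal-approximation lower limit with 80 positives and no bias is 0.60 − 1.96·√(0.24/80) = 0.493; for 0.75 it is 0.655, and for 0.85 it is 0.772. Only the first is close. With e = 5% and full agreement it becomes 0.615 − 1.96·√(0.615·0.385/78.9) = 0.507, which crosses 0.50. The lowest PPV in the table has a lower limit of 0.828 − 1.96·√(0.828·0.172/58) = 0.730.

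**Second scenario.** With 103 evaluable (about 90% of 115), sensitivity 0.80, specificity 0.60 and 5-20% of PET-discordant biopsies re-called to agree with PET, sensitivity becomes 0.81-0.84. PPV moves from 0.824 to 0.832-0.859 at 70% prevalence, and from 0.919 to 0.923-0.935 at 85%. The lowest lower limit without re-calling is 0.708, so no decision changes.

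**The case against.** The strongest objection is that the image result in the 2×2 table is each central reader's call, made blind to pathology. A local pathologist could know at most the site's own read, which dilutes the effect and can reverse it for PPV. This stands. A reader might infer that both measures must be inflated; Step 2 shows that this does not follow for PPV. It also makes the Step 1 figures upper bounds. The equivocal share, prevalence and benign-positive rate have no source in the documents either.

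Second, a reader might infer that Cohort B pathologists are given the PET result, or that nothing prevents it. The documents say neither. Site pathology follows a Pathology Manual (Protocol 10.5) and biopsy an Image Guided Biopsy Manual (Protocol 10.1.4 and 10.4), and either may contain such a rule. What can be said is that the protocol and SAP do not state one.

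Third, a reader might infer a threat to the trial's main result. There is none: Cohort A node histology is covered by the rule. Cohort B has no power calculation (Protocol 12.1, SAP 4.3) and lies outside the stated type I error control (SAP 7.5).

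Fourth, the bias need not be undetectable for ever. A later masked re-read of slides could reveal it, but none is planned.

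What survives is that the scope of a written rule omits the reference standard for two secondary accuracy endpoints, with no reason given.

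**Conclusion.** The point holds as a gap in scope. As written, the blinding rule does not reach the site pathologists who determine Cohort B truth or, read literally, Cohort A gland histology, although the same surgical work-up probably covers the gland in practice.

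The likely consequence, if PET results are known and cores are equivocal, is modest upward bias in Cohort B sensitivity: at most about 1-6 points on the assumed inputs. PPV could rise by up to 0.6-3.4 points under full site-central agreement, and could be flat or slightly lower otherwise. Against 0.50, the conclusion is at risk only near a true sensitivity of 0.60. These sizes are conditional on the assumptions listed and do not show that bias will occur. The change is worth making because the gap is clear and closing it is cheap; it is not a defect in the primary analysis.

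**What to change.** 1. Keep the existing sentence for the primary endpoint in Protocol 8.4 and SAP 4.1.
2. Add to both: local pathologists who produce histopathology for any other diagnostic-performance endpoint (Cohort A prostate gland, Cohort B biopsy) stay blinded to the study 18F-DCFPyL PET/CT result until the pathology report is final. The pathology request may give anatomic site and clinical history, including conventional imaging, but not the study PET result. Simply extending the blinding to all imaging would not work in Cohort B, where eligibility rests on radiologic evidence of disease (Protocol 7.1) and the clinical history would ordinarily disclose it.
3. Reconcile the SAP 4.1 statement that makes Cohort B biopsy depend on a positive PET lesion with Protocol 7.1, which enrols subjects already scheduled or to be scheduled for biopsy, and with SAP 5.5.7.2, which provides for biopsied lesions without PSMA-positive uptake. While it stands, the biopsy itself signals a positive scan and step 2 cannot fully blind.
4. Check that the two manuals say the same.

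Cost: a protocol amendment with ethics review (Protocol 14.2), a SAP edit, and the discipline at sites of keeping the PET result off the request until sign-out. No extra subjects, readers or procedures are needed, and no sample-size figure changes.
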